Aim 2: Develop an integrated microeconomic intervention for HIV prevention tailored for economically disadvantaged TGW which addresses multiple economic vulnerabilities in two U.S., HIV-prevalent, and resource-poor metropolitan areas. We will work with TGW in the Richmond, VA and St. Louis, MO metro areas as well as city and community partners (e.g., banks, government agencies, community-based organizations) to develop and test each of the proposed intervention components: supportive economic services, employment readiness training, financial education, gender transition financial supports, and economics-based HIV education targeting uptake of recent biomedical HIV prevention advances (e.g., PrEP). After the delivery of each module, a process measure will be administered that assesses the participants' qualitative and quantitative reactions to the material in that module.

Aim 3: Using a randomized experimental study design, evaluate the feasibility and preliminary efficacy of the integrated microeconomic intervention for economically disadvantaged U.S. TGW in reducing economic vulnerability and HIV sexual risk-taking. We will conduct a small experimental pilot-test of the integrated microeconomic intervention versus control with n = 50 TGW per arm with assessment of objective economic and behavioral indicators of HIV risk at 3, 6, and 9 months. As this is a two-site study, in Richmond this will include a total of 50 TGW with 25 TGW per arm.

4. * Describe the scientific benefit or importance of the knowledge to be gained:

In addition to the direct benefits of participation, this research is expected to yield important new information on developing HIV risk reduction interventions for people at high risk for infection. Thus, we feel that the benefits of participation far outweigh the risks.

The summary of the NIH expert panel that reviewed this work stated:

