Randomization. Fifty participants in each study site will be randomized to the intervention or wait-list minimal treatment control group. Assuming 80% retention, this will yield a total sample size of 80 (40 in each site). When assigning participants to treatment/control, we will use urn randomization, an adaptive randomization procedure that ensures approximately equal group sizes while approaching complete randomization.⁹⁴ Adherence to the intervention and supervision of interventionists. Sessions will be conducted in private spaces at our community partner locations according to the guidelines in the treatment manual developed in Aim 2. Facilitators will follow checklists developed for each session and will complete a post-session quality assurance form after each session. All study sessions will be digitally recorded. Study investigators will listen to the first recording of each session and provide feedback to interventionists regarding adherence and quality of administration. Thereafter, study investigators will listen to 20% of all recordings (chosen randomly) and provide feedback as needed. To ensure consistency across study site, investigators will listen to audiotapes and provide feedback for both study sites. Monthly group supervision with interventionists will be conducted by the investigators.

Tracking and retention procedures: As it is common for economically marginalized individuals to move frequently and to be financially unable to maintain consistent phone service, comprehensive tracking information will be collected and updated monthly. This information will include home addresses and phone numbers, but also email addresses, social media account information (e.g., Facebook, Instagram) and contact information for individuals who would know how to reach the participants (e.g., friends, family, health care providers, emergency shelter staff). Participants will also be asked to update contact information at the end of each intervention/assessment session. To increase session attendance, we will offset transportation costs.

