Assessment procedures and measures: Assessments will be conducted at baseline, 3 months post-intervention, 6 months post-intervention, and 9 months post-intervention. Graduated incentives will be used: \$20 for the baseline assessment, \$25 for the 3-month assessment, \$30 for the 6-month assessment, and \$35 for the 9-month assessment. In addition, individuals who complete all 4 assessments will receive a \$50 bonus. Incentives will be prorated contingent on completion of both the objective and subjective indicator outcomes.

Primary outcomes will be economic and behavioral vulnerability to HIV, both of which will be assessed via objective and subjective indicators. Objective indicators for economic vulnerability will include verification of employment, income, housing stability, and savings. Participants will be asked to show a copy or image of a recent pay stub, lease, and bank statement. We will also conduct home visits to verify stable living arrangements and will have information from employers (e.g., hours worked) for participants who are employed through the employment assistance program. Objective indicators for behavioral vulnerability will include verification of HIV testing, verification of linkage to care, verification of enrollment in PrEP (for HIV- participants) and verification of a current prescription for ARVs (for HIV+ participants). Participants will be asked to show a copy or image of a recent physician visit statement or receipt, HIV test result, and/or medication label. Pill counts will be used to assess adherence to biomedical prevention approaches.⁹⁶⁻⁹⁸ Participants will be prompted in advance to bring objective indicators to the assessments but it will also be possible for them to provide information afterwards (e.g., by taking a photo of a bank statement or prescription label and texting it to the project or during a home visit). Subjective indicators for economic vulnerability will include self-reported employment status, hours worked, income, housing status, and savings. Subjective indicators for behavioral vulnerability will include self-reported engagement in transactional sex, number of CSW transactions and partners, unprotected anal/vaginal sex, number and type of sexual partners, and self-reported substance use in conjunction with sexual activity.

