Mental health. Participants will complete the 18-item version of the Brief Symptom Inventory (BSI-18).¹⁰⁵ The BSI-18 contains well-validated scales assessing symptoms of depression, anxiety, and somatic distress. Norm information is available. This measure was internally consistent in a TGW sample in our prior work.^{25,88}

Data analysis. Due to the pilot and feasibility objectives and the size limitation of this study, emphasis of the comparative analysis of the intervention impact will focus primarily on estimation of potential mean changes associated with the intervention for planning purposes rather than confirmatory hypothesis testing. GEE models and mixed models would be ideal to use for data analysis; however, since we will be recruiting in two cities and analyzing data across four time points with a relatively small sample size (n=50 to yield final samples of 40), we will use less complex analyses for this study. Baseline characteristics of the two groups will be compared (t-tests for continuous variables, chi-square analyses for dichotomous and other categorical variables). Variables that are significantly different between the two groups at baseline will be controlled for if the sample size allows for us to do so. Two sets of primary analyses will be conducted for this small experimental trial. First, changes over time will be compared between the two groups, using repeated measures ANOVA for continuous variables (e.g., income) and McNemar♦s test for dichotomous variables

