(e.g., % engaged in biomedical prevention strategies of ARV use or PrEP). These mixed repeated measures ANOVAs will be conducted between the groups between baseline and each follow-up time point. We hypothesize that the integrated microeconomic intervention group will have reductions in economic and behavioral vulnerability to HIV relative to the wait-list minimal treatment control group. The second primary analysis will involve simple repeated measures ANOVAs for the integrated microeconomic intervention group only. While potential effects of maturation and history weaken our causal conclusions based on this analysis, because of the relatively small sizes of our two groups we feel it will validate our results of the mixed repeated measures ANOVA between the groups. We will use intent-to-treat analyses, using standard assumptions for those in the intervention group lost to follow-up. We will have .88 power to detect a medium effect size ($f^2 = .25$) for repeated measures ANOVA (assuming $r = .5$ for outcomes over time) and .8 power to detect a medium effect size ($f^2 = .15$ or the equivalent of partial $R = .36$) with three predictors for multiple regression. We will also compute effect sizes for use in future power analyses.

During Aim 3, we will also recruit a small number of individuals (10 total across study sites, 5 in Richmond) who report discrimination from religious organizations on the baseline assessment to participate in 60-90 minute qualitative interviews assessing those experiences. These will be digitally recorded and transcribed for qualitative analysis, similar to Aim 1. All protections used in Aim 1 will also be used here. The qualitative interview guide has been uploaded.

8. * The IRB only reviews research procedures, so differentiate which of the study procedures are:

- a. Being performed exclusively for research purposes (i.e. they would not otherwise be done apart from this study).**
- b. Alterations of routine procedures (e.g. the study is altering the timing, frequency, method, location, amount, etc.).**
- c. Being done for other purposes and whose data/results will be used secondarily in the study (e.g. standard medical or psychological tests, routine education practices, quality improvement initiatives, etc.).**

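### Sample size does not rule out the mixed model that the plan calls ideal; the pairwise ANOVAs that replace it ignore other visits, and the only missing-data rule is unnamed and covers one arm

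*Combined protocol and SAP*

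**What the plan says.** All places are in the combined protocol and SAP, Study Procedures, item 7, Specific Aim 3, unless stated otherwise.

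- **Preferred method and reason for dropping it (Data analysis).** "GEE models and mixed models would be ideal to use for data analysis; however, since we will be recruiting in two cities". The sentence adds the four time points and a "relatively small sample size (n=50 to yield final samples of 40), we will use less complex analyses for this study".
- **Replacement.** Repeated measures ANOVA for continuous outcomes and McNemar's test for dichotomous ones. "These mixed repeated measures ANOVAs will be conducted between the groups between baseline and each follow-up time point".
- **Second primary analysis.** "The second primary analysis will involve simple repeated measures ANOVAs for the integrated microeconomic intervention group only".
- **Size and visits.** Aim 3 plans the "integrated microeconomic intervention versus control with n = 50 TGW per arm". Under Randomization: "Assuming 80% retention, this will yield a total sample size of 80 (40 in each site"). Under Assessment procedures and measures: "Assessments will be conducted at baseline, 3 months post-intervention, 6 months post-intervention, and 9 months post-intervention".
- **Missing data.** Data analysis, and Study Population item 3, promise intent-to-treat analysis with conventional but unspecified assumptions for women lost from the intervention group. Nothing is said about women lost from the control group.
- **Baseline.** Variables that differ significantly at baseline are controlled for if the sample allows. No routine adjustment for the baseline value of the outcome is planned.
- **Purpose.** Estimation for planning comes ahead of hypothesis testing, and the effect sizes are to feed later power calculations.

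**The concern.** The plan gives up the method it considers best for a reason that its own numbers do not support. A woman seen at 3 months and lost afterwards adds nothing to the pairwise 6- or 9-month comparison, although her 3-month result carries information about what is missing. The plan expects 20% loss.

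Loss related to outcome is plausible here. The tracking section says that economically marginalised participants move often and cannot always keep phone service, and economic vulnerability is a primary outcome. Loss could also differ by arm. One arm gets six sessions at once plus vouchers and a wage offset; the other gets a shorter workshop, six months later according to the recruitment email. A shifted or needlessly imprecise estimate would pass straight into the planning of the next trial.

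**Working it through.** **1. The plan's power figure.** Alpha .05 is assumed, since none is stated. For a between-groups repeated measures ANOVA, λ = f²·N·m / (1 + (m−1)r). With f = .25, N = 100, m = 4 visits and r = .5: λ = .0625 × 100 × 4 / 2.5 = 10 on 1 and 98 df, power .879. The stated .88 is reproduced if .25 is f, not f² as printed. A two-visit within-subject test in 40 women also gives λ = .0625 × 40 × 2 / .5 = 10, on 1 and 38 df, power .869. The figure therefore does not show which analysis was powered, and nothing below depends on it.

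**2. Can the data carry the model?**
- Fixed effects: 4 visit means (common baseline) + 3 arm-by-visit terms + 1 site term = 8.
- Unstructured covariance: 4 × 5 / 2 = 10. Total 18 parameters.
- Observations: up to 100 × 4 = 400. If 80 women complete everything and 20 give only a baseline, 100 + 3 × 80 = 340.
- A pairwise ANOVA on 80 women uses 80 × 2 = 160 values.
- In simulation (N = 100, four visits, about 20% dropout) the unstructured model converged in every trial where convergence was recorded, also at N = 50. Test size was .043 to .063.

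**3. Precision.** With two visits, the group-by-time test is a t test on change scores. With SD 1:
- variance of change: 2(1 − r) = 1.00 at r = .5
- variance after baseline adjustment: 1 − r² = .75
- SE ratio: √(.75/1.00) = .866, a 13% reduction
- with 40 per arm: √(2/40) = .224 against √(.75 × 2/40) = .194

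Simulated 6-month SEs were .213 (change score), .184 (baseline-adjusted ANCOVA) and .186 (mixed model). The gain is baseline adjustment; the extra visits add none.

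**4. Between-arm bias.** Set-up: 50 per arm, r = .5, true effect .30 SD, higher scores better, about 76% to 79% retained. The assumed logit slope of dropout on the previous visit is 1.0 to 1.5 per SD, with worse-off women leaving. The ANCOVA row is from a parallel run of the same set-up.

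| Dropout depends on previous visit | Analysis of available women | 6 months | 9 months |
|---|---|---|---|
| in controls only | pairwise ANOVA | .34–.36 | .32–.35 |
| in controls only | ANCOVA on baseline alone | .27–.28 | .25–.26 |
| in controls only | mixed model | .29–.31 | .29–.31 |
| same rule in both arms | pairwise ANOVA | .29–.31 | .29–.31 |

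The parallel run put the pairwise ANOVA at .33 to .35 at 6 months.

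Why the sign is positive: if low-baseline controls leave, the baseline mean of those who stay rises by some s, but their expected follow-up mean rises only by r·s = .5s. Their change falls by .5s, and the arm difference grows. If better-off controls left, the sign would reverse. ANCOVA removes this part but not the dependence on later visits, so it errs the other way.

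**5. Other assumed mechanisms.**
- Dropout after 3 months depends on change so far, differently by arm, true difference 0: completers' ANOVA about +.18 SD (r = .5) or +.10 SD (r = .7), rejection .08 to .13. Mixed model −.01 to .00, rejection .05 to .06.
- The same rule in both arms: between-arm bias within about .04 SD. The intervention-only ANOVA on completers is still off by +.05 to +.13 SD when the true change is 0.
- If the unnamed rule meant last value carried forward in the intervention arm only (one possible reading), a common dropout rule and a true difference of 0 give −.10 to −.22 SD, rejection .09 to .17.

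**The case against.** **The plan does address missing data.** A reader might infer that the ANOVAs use only women seen at the visit. The documents do not say so: the intent-to-treat sentence implies some handling of losses in the intervention arm. Analysing only available women in the control arm is an inference from silence. What stands is that the rule is unnamed and covers one arm.

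**The ANOVA is not biased merely because dropout depends on earlier results.** This stands for the between-arm contrast. The bias needs a dropout rule that differs by arm, and no document says that it will.

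**The precision gain is not a mixed-model gain.** This stands; baseline-adjusted ANCOVA gives the same SE. The case for the mixed model over ANCOVA is the bias in step 4.

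**Four complete visits are not required.** A reader might infer that women missing any visit are dropped from the between-arm analyses. Those are pairwise, so they are not.

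**The bias is small for a pilot.** It is .03/.213 = 14% to .06/.213 = 28% of one standard error. That limits the severity, but estimation is this trial's stated product.

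**Small size does matter for some outcomes.** This partly stands. The parameter count covers a linear model only. Binary outcomes and counts need small-sample care, and group delivery adds clustering that the count leaves out.

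**Conclusion.** The point holds in a limited form. One hundred randomised women with four visits are enough for a linear mixed model of the continuous outcomes, so the stated reason for choosing pairwise ANOVAs fails there. Those ANOVAs ignore the other visits and do not routinely adjust for baseline, and missing-data handling is unspecified for controls and unnamed for the intervention arm.

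The between-arm bias is conditional. It is about .03 to .06 SD on a true .30 SD when only control dropout depends on earlier results, up to about .18 SD under a harsher assumed mechanism, and near zero when both arms follow the same rule. The intervention-only analysis is biased even then. The SE reduction of about 13% assumes r = .5 and comes from baseline adjustment. All dropout slopes are assumptions. The mixed model is itself unbiased only if dropout depends on observed data and the model form is adequate. The plan should be changed, but this is not a flaw that invalidates the trial.

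**What to change.** Replace the separate between-arm ANOVAs with the following.

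- **Continuous outcomes:** one linear mixed model each, on all randomised women with any assessment. Include a common baseline mean, visit, arm-by-visit and site, unstructured covariance and Kenward-Roger degrees of freedom. Name a simpler covariance structure in advance as the fallback. Report the arm difference at each visit with its 95% CI. Within-arm change in the intervention group can be read from the same model.
- **Skewed income and counts:** transform, or use a model suited to their distribution.
- **Binary outcomes:** GEE with a small-sample correction. McNemar's test compares paired proportions and does not by itself compare arms.
- **Missing data:** replace the unnamed assumptions with the mixed model as the main analysis, plus one stated sensitivity analysis applied to both arms.

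The cost is SAP wording and standard software; no data collection changes. The downside is that a sparse outcome may fail to converge, which is why the fallback must be written down first.

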This will include 30 TGW (15 in each site) for qualitative interviews which we believe will be enough to achieve saturation, 20 TGW (10 in each site) for pilot testing of intervention (we believe this will match the size of the intervention group and thus is appropriate for intervention piloting), and 100 TGW (50 in each site) for the randomized controlled trial. The total number above also reflects the numbers we anticipate screening for study inclusion. This will include some individuals who are not eligible and some individuals who are eligible but choose not to participate in study activities other than completing the screening survey. For the RCT the size is justified by power analysis. We will use intent-to-treat analyses, using standard assumptions for those in the intervention group lost to follow-up. We will have .88 power to detect a medium effect size ($f^2=.25$) for repeated measures ANOVA (assuming $r = .5$ for outcomes over time) and .8 power to detect a medium effect size ($f^2 = .15$ or the equivalent of partial $R = .36$) with three predictors for multiple regression.

4. * List the study inclusion criteria:

For screening, inclusion criteria will include that the participant is a transgender woman and is 18-45 years of age.

For TGW, full study participation, inclusion criteria will require both (i) Economic vulnerability (unemployment or underemployment [less than 20 hours/week], low income [less than the Medicaid poverty threshold], housing insecurity in the past year, or food insecurity in the past year), and (ii) Behavioral vulnerability to HIV transmission: unprotected sex in prior 6 months, transactional sex, multiple sexual partners, 1-time sexual partner, sex with a partner of unknown HIV status, sex under the influence of drugs or alcohol. Participants will be recruited if they are age 18 or older. Based on our prior work, we expect participants meeting these guidelines to be relatively young (mean age = 32, SD =10) and predominantly African American. Based on data from our pilot work, we expect around 45% of individuals screened to meet eligibility requirements.

These are the inclusion criteria for TGW for Aims 1, 2, and 3.

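### Continuous outcomes: pre-specify ANCOVA on the baseline value, with site, instead of a change-score ANOVA with covariates picked by baseline significance (intervals about 13% narrower at r = .5 if SDs are equal)

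*Combined protocol and SAP*

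**What the plan says.** All of this is in Study Procedures, item 7, Specific Aim 3, Data analysis, unless another place is named.

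- Change is compared between arms "using repeated measures ANOVA for continuous variables (e.g., income" being the example given).
- Each such analysis uses two time points: "These mixed repeated measures ANOVAs will be conducted between the groups between baseline and each follow-up time point".
- The one rule on covariates is "Variables that are significantly different between the two groups at baseline will be controlled for if the sample size allows". Baseline comparisons are by t-test or chi-square. The plan states no significance level and does not say what sample size would allow adjustment.
- The stated emphasis is "estimation of potential mean changes associated with the intervention for planning purposes rather than confirmatory hypothesis testing".
- The power statement assumes r = .5 over time and also covers a regression "with three predictors for multiple regression. We will also compute effect sizes for use in future power analyses". No regression analysis is described and its three predictors are not named.
- The Randomization paragraph says "Fifty participants in each study site will be randomized to the intervention or wait-list minimal treatment control group". Aim 3 in Background, Rationale and Goals, item 3, adds "As this is a two-site study, in Richmond this will include a total of 50 TGW with 25 TGW per arm". The urn scheme is not said to be stratified by site.

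The documents give no SDs for any outcome.

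**The concern.** With two arms and two times, the group-by-time test is a comparison of mean change. A change score subtracts the whole chance difference in the baseline outcome. When the SDs are equal and r is below 1, that is more than the follow-up value would be expected to carry, so the estimate over-corrects for whatever imbalance the randomisation happened to produce. Over repeated randomisations the estimate is unbiased. The loss is in precision.

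The covariate rule does not repair this. A significant baseline difference between randomised arms is chance, and a strong predictor that happens to be balanced is never admitted. The final model is known only after the baseline data have been examined. Site, which is part of the design, would almost never qualify.

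What is at stake is the width of the between-arm interval and an adjustment set fixed in advance. The plan intends to carry its effect sizes into later power calculations, so these are what this analysis has to deliver. The point does not concern the dichotomous outcomes sent to McNemar's test or the intervention-only analysis.

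**Working it through.** **Inputs.** From the plan: r = .5; 50 per arm randomised; 80% retention, so 80 analysed (40 per arm if losses are equal). Assumed, because the plan is silent: two-sided alpha .05, and equal SDs at baseline and follow-up for the main case.

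**The plan's own figures.** The .88 for repeated measures ANOVA is reproduced (.879) with f = .25, N = 100, four time points and the between-groups test. Read literally as f² = .25, that test gives power above .99. Two other settings come close to .88, so its basis is not certain, and none of what follows depends on it. The .8 for three-predictor regression at f² = .15 is reproduced at N = 77 (.802); at N = 80 it is .819. That matches the retained sample.

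**Equivalence.** In a simulated data set the group-by-time F and the squared change-score t were both 0.2115.

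**Variance.** Let k = baseline SD / follow-up SD, with follow-up SD = 1.

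- Change score: 1 + k² − 2rk
- ANCOVA: 1 − r²
- Difference: (k − r)², which is never negative

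| r | k | Change | ANCOVA | Variance saved | CI narrower |
|---|---|---|---|---|---|
| .3 | 1 | 1.40 | 0.91 | 35% | 19% |
| .5 | 1 | 1.00 | 0.75 | 25% | 13% |
| .7 | 1 | 0.60 | 0.51 | 15% | 8% |
| .5 | 0.5 | 0.75 | 0.75 | 0% | 0% |
| .5 | 0.75 | 0.8125 | 0.75 | 8% | 4% |
| .5 | 1.25 | 1.3125 | 0.75 | 43% | 24% |

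The last column is 1 − √(ANCOVA / change).

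**Half-width at 40 per arm, r = .5, k = 1.**

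- Change score: t(78) × 1 × √(2/40) = 1.991 × 0.2236 = 0.445 SD
- ANCOVA: t(76) × √.75 × √(2/40) = 1.992 × 0.866 × 0.2236 = 0.386 SD

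With the finite-sample ANCOVA factor the second figure is 0.388, so the interval is 12.8% narrower. At 50 per arm, on the same basis, it goes from 0.397 to 0.346 (12.9%).

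**Power for 0.5 SD, r = .5, k = 1** (noncentral t, df 2n − 2 against 2n − 4): .598 to .722 at 40 per arm, and .697 to .815 at 50 per arm. In 40,000 simulated trials with arm, baseline and site in the model and no site effect, the corresponding values were .598 to .717 and .695 to .811, with variance down 24% at 40 per arm. With k = 0.5 at 40 per arm, variance rose by 1.3%, the worst case tried.

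**What the plan's rule recovers.** In 20,000 simulated trials at 40 per arm it admitted the baseline outcome in 5.0%. Mean half-width was 0.442 under the rule, 0.444 for the plain change score and 0.387 for ANCOVA.

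**Over-correction given an imbalance:** (1 − r) × imbalance. An imbalance of z = 1.5 at 40 per arm is 1.5 × √(2/40) = 0.335 SD. The over-correction is then 0.17 SD at r = .5, 0.23 at r = .3 and 0.10 at r = .7.

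**Site under the rule.** With 40 retained per arm and per site, a 24/16 against 16/24 split gives p = .074, and 25/15 against 15/25 gives p = .025. If the site totals differ slightly, 25/15 against 16/24 gives p = .044. With 25 per arm planned in Richmond, splits that uneven are unlikely.

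**The case against.** The strongest objection is that 13% depends on SDs the documents do not give. Income is the plan's own example of a continuous outcome, and entry requires "Economic vulnerability (unemployment or underemployment [less than 20 hours/week], low income [less than the Medicaid poverty threshold"]) or another qualifying hardship. Baseline spread in income or hours may therefore be compressed, and the gain for those outcomes may be small. This stands, and it is why a range is shown. The self-efficacy scales and the BSI-18 are not eligibility criteria, so the argument does not reach them.

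Other points on that side:

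- **Group delivery and missing data.** Sessions are run in groups. With an assumed ICC of .05 and groups of 10 in both arms, the variances become 1.45 and 1.20, and the standard error falls about 9%. If clustering is in one arm only, it falls about 11%. If 20% of values were baseline carried forward, r would rise to about .6 and the gain would be about 11%. These inputs are assumptions, and a gain remains in each case. The quoted power values would be too high under clustering.
- **The z = 1.5 example is not typical.** The median |z| of 0.67 gives about 0.075 SD. If applied, the rule also admits the baseline outcome once its difference is significant, which caps the over-correction near 0.22 SD. Both points are correct.
- **The rule is written in advance and uses baseline data only.** True: this is not selection on outcomes. The discretion lies in the unstated significance level and in the sample-size proviso.
- **Site has no demonstrated precision gain, and the powered regression may signal an intended adjusted analysis.** No gain from site is claimed here. An undescribed regression does not fix a covariate set.
- **Change scores match the plan's interest in mean changes.** Once the baseline value is in the model, the arm coefficient is the same whether the response is change or the follow-up value, so nothing is lost for the between-arm estimate.

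**Conclusion.** The concern holds, as a matter of efficiency and pre-specification and not of validity. It should be acted on. No part of the plan fixes the baseline outcome or site as a covariate, and the rule it does give recovers almost none of the available precision.

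The 13% figure is for one continuous outcome at one follow-up, under the plan's r = .5, with equal SDs, independent participants and two-sided alpha .05 assumed. It comes entirely from the baseline outcome. The direction is secure, because the large-sample variance saved cannot be negative. The size will differ by outcome and may be near zero for income or hours. The gain from site cannot be computed from the documents.

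The plan sets aside GEE and mixed models because of the small sample, two cities and four time points. That reasoning does not apply to an ANCOVA at a single follow-up, which is an ordinary three-predictor regression of the size the plan already powers.

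**What to change.** For each continuous outcome, pre-specify a linear model at each follow-up with arm, the baseline value of that outcome and site as fixed terms, whatever the baseline p-values. Report the adjusted between-arm difference with its 95% confidence interval, and give arm means and mean changes alongside as description.

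Include site because recruitment and arm sizes are planned by site, not for a claimed gain in precision. Delete the significance-based covariate rule and present baseline characteristics descriptively. Leave the dichotomous and intervention-only analyses outside this change.

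The cost is wording. The baseline outcome and site are already recorded, and the model uses two more degrees of freedom. In the least favourable case tried, variance rose by about 1%.
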